2.3. POTENTIAL RISKS AND BENEFITS

2.3.1. POTENTIAL RISKS

All supplies used are sterile and disposable. Subjects will not be identified in any reports on this study. In the case of adverse events or physical injury resulting from participation in this study, subjects are provided with contact numbers for the responsible physicians and a 24-hour emergency access number to obtain immediate medical care. Records will be kept confidential to the extent provided by Federal, State, and local law. Nevertheless, subjects are informed that the sponsor and the Institutional Review Board for the use of human subjects in research may inspect the records of this investigation. Experienced personnel using the standard safety procedures employed in clinical practice will perform the catheter insertions. These include the wearing of protective gloves, use of disposable materials and medication-grade solutions. The insertion of intravenous catheters is performed by skilled personnel, including the study physicians, research nurses and nuclear medicine technology staff. In over several years of practice, we have encountered no serious complications from intravenous cannulations. In the very unlikely event of vascular damage, medical or surgical treatment will be employed to minimize vascular injury. Infection at the site of cannulation will be treated with appropriate systemic antibiotic therapy or with surgical intervention. Idiosyncratic responses to the study radiopharmaceuticals are unlikely at the tracer doses employed, however, we will exclude subjects with prior history of allergic response to the study tracers, or chemically related drugs. A "crash cart" is immediately available in the PET suite, containing necessary drugs for management of allergic or other drug reactions. A physician is immediately available in the PET suite or in the immediately adjoining Nuclear Medicine Clinic area at all times when research subjects are present. The lowlevel radiation exposure arising from participation in the studies in this project is well within Federal guidelines established for participation of normal adult volunteers in medical research involving radiation. All subjects will be encouraged to drink plenty of fluids after the studies to encourage voiding and further diminish radiation exposure to the urinary tract and kidneys. During the performance of the studies, the volunteers will be monitored at all times by research personnel associated with the project (research coordinator, research assistants, radiology technologists) or the investigator. All volunteers will be provided the phone numbers for the Principal Investigator and the Research Coordinator in the consent form. A copy of the consent form is provided to each subject, who will be encouraged to contact the investigator if they notice any unusual symptoms or untoward side effects. The investigator has ample prior experience in the utilization of these procedures.

HD-tDCS

Transcranial Direct Current Stimulation (tDCS) is a safe technique that poses a nonsignificant risk to participants. The safety of this technique has been addressed and tested by multiple researchers (e.g., (Nitsche, Fricke et al. 2003; Nitsche, Liebetanz et al. 2003; Nitsche, Liebetanz et al. 2003; Priori 2003; Nitsche, Niehaus et al. 2004; Hummel and Cohen 2005; Iyer, Mattu et al. 2005; Fregni, Boggio et al. 2006)) who have concluded that tDCS, as applied in a manner similar to our proposed protocol, induces only temporary cognitive/motor effects, and no negative side effects. More than 30 research studies involving hundreds of participants have been published using tDCS. Hundreds more participants have undergone tDCS for unpublished pilot research (Nitsche, Liebetanz et al. 2003). No undesirable or long-lasting effects have been reported, nor have any participants reportedly abandoned a study due to discomfort. Researchers at the National Institute of Neurological Disorders and Stroke (NINDS)(Iyer, Mattu et al. 2005) conducted a safety study on our tDCS protocol. investigating 20minute sessions of 1 mA and 2 mA current stimulation with healthy controls (n=103). No negative effects were identified. Nitsche and colleagues (2004) found no measurable structural changes in brain tissue due to tDCS (Nitsche, Niehaus et al. 2004). Additionally, other studies (Fregni, Boggio et al. 2005; Hummel and Cohen 2005) have shown that tDCS can be used safely in stroke patients and in patients with major depression (Fregni, Boggio et al. 2006; Boggio, Rigonatti et al. 2007). In these studies only mild adverse effects, such as mild headache, have been reported. Finally, two recent studies showed that several sessions of tDCS are safe to be used in chronic pain syndromes, including one from our group in migraine (DaSilva et al. 2012), fibromyalgia and spinal cord injury (Fregni, Gimenes et al. 2006, Fregni, Boggio et al. 2006). Thus, a growing body of research from different laboratories has shown that tDCS is a safe, noninvasive, and painless technique for modulating neural excitability, with measurable but only transient effects. The protocol described in our study uses stimulation levels that fall well within safety limits established by basic research investigating neural tissue damage, as well as numerous studies applying (HD)-tDCS with human participants (Yuen, Agnew et al. 1981; McCreery, Agnew et al. 1990; McCreery, Agnew et al. 1990; Nitsche, Liebetanz et al. 2003). For more safety information on (HD) tDCS please see the following links:

tDCS (http://www.jove.com/details.php?id=2744) [DaSilva et al., 2011a]

and

HD-tDCS (http://www.jove.com/video/50309/technique-considerations-use-4x1-ring-high-definitiontranscranial) [Villamar et al., 2013]

PET

Potential risks to the subjects participating in these studies include those associated with MR and PET imaging. Prior to inclusion in the study, the presence of potential MR

risks, such as pacemakers, surgical clips or metallic surgical devices will be excluded by medical and surgical history using a standard review form. Potential PET risks include potential complications or inconveniences associated with venous cannulation, the administration of study radiopharmaceuticals, and the exposure to low level radiation. The radiation exposure resulting from these studies is well within that associated with routine radiological procedures and is not associated with adverse health consequences.

A 15 mCi injection of [11C]CFN will result in a whole body effective dose equivalent of 0.26 rem, which is less than 6% of the dose that occupationally exposed individuals are permitted to receive each year, and a critical organ (liver) mean dose equivalent of 0.89 rem. Completion of the maximum number of PET scans (four) will result in a whole body dose equivalent of 1.82 rem, which is 36% of the dose that occupationally exposed individuals are permitted to receive each year.

The proposed PET methods have no alternatives for collection of the necessary data at the present time. There are no serious risks associated with the intramuscular infusion of the salt solution. A known risk includes the possibility of puncturing a blood vessel.

QUANTITATIVE SENSORY TESTING

For both migraine subjects and healthy volunteers, thermal quantitative sensory testing will be performed in four areas: the right and left supraorbital area (temple), and dorsum of the hands.

We will use a standard clinical evaluation program designed for the Pathway system (MEDOC-Israel). This program is comprised of a series of hot and cold stimuli that are delivered from a baseline temperature of 32°C, bilaterally. The subject will control the heating/cooling unit with a computer mouse. They will be instructed to tap the mouse button at the first perception of pain. Each stimulus (hot and cold) will be delivered three times in each location, and the Pathway program records the average temperature.

This stimulus, though it may feel mildly painful, does not produce any skin damage. The QST is not associated with pain lasting beyond the study period nor with any irreversible damage to the body.

Infusion/Blood Collection

Puncturing of a blood vessel results in bruising and can be accompanied by minor swelling and pain. The condition is treated by icing and typically resolves in a few days. According to our records, since 1989, puncturing of a blood vessel occurred in two of more than 600 infusions.

Subjects may feel a slight needle prick when blood is drawn. Some patients may have a slight bruise that will go away within a few days. Sometimes, patients feel light headed

or feel dizzy. Other rare complications associated with the blood sample collection include:

- Infections
- Nerve lesions
- Accidental arterial puncture (when the needle pierces an artery instead of a vein).

Genetic Research/Confidentiality

Genetic research may provide information about who is at risk to develop the disease. Some people may find this information stressful or uncomfortable. While our research is focused primarily on pain mechanisms through new genetic technologies that allow us to look at all of the information across the genome, we may learn information about subjects regarding diseases not related to pain. We do not intend to release the results of the genetic testing to subjects.

If multiple members of a family are enrolled in research, information from this research may identify previously undisclosed biological relationships (i.e. non-paternity or non-maternity).

It is unlikely, but there is a possible risk of breach of confidentiality. The databases developed for this project will not contain information that is traditionally used to identify subjects, such as name, address, telephone number, or social security number. It is also possible that there could be violations to the security of the computer systems used to store the codes linking genetic and medical information to subjects. These codes will be maintained only at the University of Michigan.

2.3.2. KNOWN POTENTIAL BENEFITS

Participation in this study may help determine whether molecular mechanisms and their modulation are in effect to suppress pain in patients suffering from episodic migraine. Direct and longterm benefits to the subjects participating in the studies are not anticipated. Subjects will be informed that the medical significance of these studies is presently unknown, and that the results will not influence their subsequent medical care.

3. OBJECTIVES

3.1. STUDY OBJECTIVES

Objective #1:

To demonstrate that clinical and experimental pain measures in migraine patients are associated with µOR BPND in the thalamus and other pain-related regions, even during interictal phase (non-headache phase).

Objective #2:

To determine whether 10 daily sessions of M1 HD-tDCS have modulatory effect on clinical and experimental pain measures in migraine patients.

Objective #3:

To investigate whether repetitive active M1 modulation induces/reverts thalamic µOR BPND, and whether those changes are associated with clinical and experimental pain measures in migraine patients.

3.2. STUDY OUTCOME MEASURES

3.3. PRIMARY OUTCOME MEASURES

We hypothesize that migraine patients will have a reduction in thalamic μ OR BP_{ND} at the baseline level (see preliminary data). The activation of μ OR neurotransmission, calculated as reduction in μ OR BP_{ND} during a sustained thermal pain threshold stress challenge will also be lower than in controls, and that both these measures will be associated with clinical and experimental pain ratings.

3.4. SECONDARY OUTCOME MEASURES

Our hypothesis is that 10 daily sessions of active M1 HD-tDCS modulation will induce analgesic after-effect in clinical and experimental pain measures. The focused targeting of M1 with HD-tDCS will lead to precise sensory-discriminative modulation of pain (area and intensity). This will be evidenced in our questionnaires, tracking tools, and quantitative sensory tests.

We hypothesize that after 10 M1 HD-tDCS sessions there will be an increase in μ OR BP_{ND} (return toward healthy control values) in the thalamus and other pain-related brain areas in migraineurs at follow up, along with reductions in clinical/experimental pain measures.

4. STUDY DESIGN

This is a phase 2, single center, three-arm, double-masked, randomized investigation of the modulation of the μ -opioid mechanisms in episodic migraine (in vivo).

The population for the study will consist of 60 patients with episodic migraine (30 for the active M1 HD-tDCS group and 30 for the placebo HD-tDCS group). In addition, we will use the data from up to 10 healthy controls who were recruited and scanned during the NINDS-K23062946 project (IRBMED #HUM00027383; [name], Principal Investigator). We will then recruit healthy volunteers to a total of 30 age- and gender-matched healthy subjects.

All subjects will be enrolled as either episodic migraine or healthy volunteers (HV; N=90); if episodic migraine (n=60), they will be randomized to one of two treatment arms: active (n=30) or sham (n=30).

Each participant will undergo the sequence of events and evaluations laid out in the Schematics of Study Design (Protocol Summary; pages vii-viii), which will take approximately 3 months. Completion of full protocol enrollment and participation is expected to take approximately 5 years.

Data will be collected either on paper or electronic CRFs (most questionnaires, screening/demographic and logistical information regarding assessments) or electronically on local systems(PET, MRI, HD-tDCS), then transferred via HIPAA-compliant methods within the UMHS system for analysis by study staff.

5. STUDY ENROLLMENT AND WITHDRAWAL

5.1. SUBJECT INCLUSION CRITERIA

In order to be eligible to participate in this study, an individual must meet all of the following criteria:

- Provide signed and dated informed consent form
- Willing to comply with all study procedures and be available for the duration of the study
- Male or female, aged 18 to 65, inclusive, and
- Meet criteria for an "episodic migraine" patient:
 - Episodic migraine (ICHD-3-beta) with at least one attack per month and less than 15 attacks per month
 - Migraine for at least 6 months
 - No intake of opiate medication for the past six months
 - No overuse of analgesic medication, defined as regular intake on
 ≥15 days per month for more than 3 months
 - Willing to limit the introduction of new treatments for headache management

OR

- Meet criteria as a Healthy Volunteer:
 - Without medication overuse
 - Without self-reported history of systemic disorders or other pain disorders, including migraine.

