5.2. SUBJECT EXCLUSION CRITERIA

An individual who meets any of the following criteria will be excluded from participation in this study:

- Presence of any other systemic or chronic pain disorder
- History or current evidence of a psychotic disorder (e.g. schizophrenia) or substance abuse; bipolar or severe major depression, as evidenced by Beck Depression score of ≥ 20*
- Prior use of tDCS
- Ongoing, unresolved disability litigation
- History of neurological disorder (e.g. epilepsy, stroke, neuropathy, neuropathic pain)
- Current use of opioid pain medications
- Allergic response to study radiotracers or chemically-related drugs
- Excluded by MRI Center or PET Center safety screening checklist (as administered by study staff)
- Female participants who are pregnant, nursing, or planning a pregnancy, or who are of childbearing potential and are not using a reliable means of contraception during the baseline and study periods (negative urine pregnancy test must be available before any procedures are initiated)
- Treatment with an investigational drug, device or other intervention within 30 days of study enrollment (Screening Visit).
- Anything that would place the individual at increased risk or preclude the individual's full compliance with or completion of the study (eg, medical condition, laboratory finding, physical exam finding, logistical complication).

^{*} The Beck Depression Inventory will be graded by study staff at the time of completion. Individuals with a score of ≥ 30 will be provided with a pamphlet from the Michigan Depression Center that contains information and contacts regarding depression. In addition, those individuals who respond to question #9 with answers #2 or #3, will be provided with a flyer from the Department of Health and Human Services National Suicide Prevention Lifeline (800 number and website).

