8.2. LABORATORY EVALUATIONS

8.2.1. CLINICAL LABORATORY EVALUATIONS

Pregnancy and drug screen testing will be performed by dipstick analysis. The results of each test will be immediately related to the subject and if positive, a repeat test may be performed on a second sample. These coded research results will be recorded in a file that is kept separately from the rest of the research data.

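### The six-month opiate-free rule covers migraine patients only, so a healthy control with recent past opioid use can enter the primary mu-opioid receptor comparison

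*Combined protocol and SAP*

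**What the plan says.** Section 5.1 gives a few requirements for everyone and then two alternative branches.

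- **Migraine branch.** It includes "No intake of opiate medication for the past six months". It also bars analgesic overuse, defined as regular intake on "≥15 days per month for more than 3 months".
- **Healthy-volunteer branch.** It has two items: "Without medication overuse", not further defined there, and "Without self-reported history of systemic disorders or other pain disorders, including migraine". Neither mentions opioids.

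Section 5.2 applies to all subjects. Its relevant exclusions are "Current use of opioid pain medications" and "History or current evidence of a psychotic disorder (e.g. schizophrenia) or substance abuse".

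Section 8.2.1 adds that "Pregnancy and drug screen testing will be performed by dipstick analysis". Appendix A places this at the PET visits, and a footnote describes it as a safety screen for the tracer. Appendix A also schedules medication history at screening and concomitant medications at the first imaging visit.

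The primary hypothesis in Section 3.3 is that patients have reduced thalamic mu-opioid receptor binding potential at baseline, and that activation under the pain challenge "will also be lower than in controls". Section 4 plans 60 patients and 30 controls, with up to 10 of the controls taken from an earlier project.

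**The concern.** The outcome is binding at the mu-opioid receptor, so past opioid intake is an obvious characteristic to hold alike in the two groups. The eligibility rules hold it alike only for use that is current. For use that ended within the previous six months, one group is restricted and the other is not.

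Age and gender matching does nothing about this. The Aim 1 model in Section 11.1 adjusts for age and other nuisance variables, with estradiol and proximity of attacks as examples; prior opioid use is not named. The control values are also the benchmark for the post-treatment hypothesis in Section 3.4, which expects patients to move back towards them. A difference in opioid history between the groups could therefore affect both the primary contrast and the reading of the treatment result.

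**Working it through.** **Step 1: a test case against each rule.** Take a healthy volunteer who finished a short prescribed opioid course a few weeks before screening.

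- Six-month rule (5.1, migraine branch): does not apply to this person.
- Medication overuse (5.1, volunteer branch): undefined there. On the patients' definition, a short course does not reach 15 days a month for more than three months.
- Self-reported systemic or pain disorder (5.1): silent on past medication.
- Current opioid use (5.2): not met, because the course has ended.
- Substance abuse (5.2): short prescribed use is not abuse.
- Dipstick at PET (8.2.1): the panel is not stated, no six-month look-back is set, and the only follow-up given for a positive result is an optional repeat test.
- Medication history (Appendix A): may record the course, but no criterion turns the record into an exclusion.

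The volunteer is eligible. A migraine patient with the same history fails at the first line.

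**Step 2: how many controls.** No exposure rate is given, so 5–15% is an assumption. Section 14.4 has 20 controls newly recruited and 10 carried over.

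- 0.05 × 20 = 1
- 0.15 × 20 = 3

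That is 1 to 3 newly recruited controls, against none of the 60 patients by rule. If fewer than 10 controls are carried over, the number recruited under the current wording rises accordingly.

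**Step 3: what that could do to the contrast.** No figure in the plan depends on the rule, so this is illustration only. If k of n controls are shifted by s standard deviations, the control mean moves by (k/n) × s. Take n = 24, the per-group number in Section 11.2, and assume s between 0.5 and 1.0 with the standard deviation unchanged.

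- k = 1, s = 0.5: (1/24) × 0.5 = 0.02 SD
- k = 3, s = 1.0: (3/24) × 1.0 = 0.125 SD

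A downward shift in controls would shrink the expected difference by that amount; an upward shift would widen it. For the shrinking case, power was computed for a two-sided t-test at 0.05 with 24 per group:

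| True effect (SD) | No shift | 0.02 SD lost | 0.125 SD lost |
|---|---|---|---|
| 0.83 | about 80% | 78.4% | 66.7% |
| 1.2 | 98.3% | 97.9% | 95.4% |

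Section 11.2 states 80% power at 1.2, which does not reproduce. That is a separate matter and does not bear on this point.

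**The case against.** The opposing case has four parts.

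- **Motive.** A reader might infer that the sponsor set the rule because it regards past opioid intake as a threat to the binding measure. The documents do not say so. The rule stands among items that define the migraine population, such as attack frequency, duration and analgesic overuse. The reference list includes titles on opiates and headache. A purpose of defining a clean migraine group is just as plausible, and the asymmetry may be deliberate. This stands.
- **Permission is not exposure.** A reader might infer a systematic difference in opioid history. The text shows only that exposed controls can enter, not that they will. Controls must report no systemic or pain disorder, and the overuse, abuse and current-use rules thin the field further. This stands.
- **Carried-over controls.** A reader might infer that these were never checked. Their earlier criteria are not given and may have been the same or stricter. For that reason the assumed rate should not be applied to all 30 controls, which would give 1.5 to 4.5.
- **Other safeguards.** The phone prescreen, the PET Center checklist and the Manual of Procedures are not available here and might ask about past use. The covariates named for Aim 1 are only examples. This stands in part. Staff could record the history, but no stated criterion acts on it. Adjustment would also help little: if only controls can be exposed, an exposure indicator in a linear model leaves the group contrast resting on patients against unexposed controls, much as if the exposed controls had been dropped.

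None of this closes the gap in the eligibility text.

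**Conclusion.** The point holds as a gap in eligibility. The six-month look-back binds patients only, and no stated rule keeps a control with recent past opioid use out of the primary comparison. It is worth correcting because the outcome is mu-opioid receptor binding itself and the correction is cheap.

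Its practical size is uncertain. The count of 1 to 3 among 20 new controls rests on an assumed 5–15% rate. The documents do not show that an opioid course some weeks earlier changes binding, by how much, for how long or in which direction. On the assumed shifts, the loss of power is small at the plan's effect size of 1.2 and moderate at 0.83. The point does not show that the comparison is biased.

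**What to change.** Move the existing six-month criterion in Section 5.1 from the migraine branch to the criteria common to all subjects, so that newly recruited healthy volunteers meet the same requirement. This extends the protocol's own rule and introduces no new one.

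For the up to 10 carried-over controls, check the existing records for opioid use in the six months before their scan. Then repeat the Aim 1 comparison without any control whose history is positive or unknown. They need not be rescanned or replaced.

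The cost is a short amendment, one added screening question, a few healthy candidates deferred and a records check. The sensitivity analysis has fewer controls. In the extreme case where all 10 carried-over histories are unknown, it compares 60 patients with 20 controls in place of 30. Before dropout, the standard error in SD units rises from √(1/60 + 1/30) = 0.224 to √(1/60 + 1/20) = 0.258, about 15%.

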Potential pitfalls and alternative strategy: Regarding possible negative results we have to explore other scenarios: First, our hypothesis was wrong. However, this is unlikely due to extensive data from our group showing decreased levels of μOR BP_{ND} in chronic pain, including our initial migraine and allodynia data (DosSantos et al., 2012; DaSilva et al., 2014a; Nascimento et al., 2014a). Nonetheless, if the migraine mechanisms are not through a change in the μ-opioid system we need to explore alternative mechanisms in the future, such as the glutaminergic and GABA systems—data which will also be acquired during this study (see Aim3 alternative strategy)— hence, the results will still be interesting to report and investigate further. Second, μOR BP_{ND} levels at baseline will not be correlated with pain levels (also unlikely based on our data) (DaSilva et al., 2014a; DosSantos et al., 2014a). Although we are powered to perform all the analyses in this study, correlation analysis is a test that has low power. In the case of a statistical trend for a correlation, we will look at thalamus and other pain-related regions, and consider increasing the sample size by 20% and then describing these specific results as exploratory. We will also use different pain ratings (e.g., Pain Trek).

Does M1 HD-tDCS have modulatory effect on experimental and clinical measures in migraine?

Aim 2. To determine whether 10 daily sessions of M1 HD-tDCS have modulatory effect on clinical and experimental pain measures in migraine patients.

Our hypothesis is that 10 daily sessions of active M1 modulation, as compared to sham, will induce a greater analgesic after-effect in clinical and experimental pain measures. The focused targeting of M1 with HD-tDCS will lead to more precise sensory-discriminative modulation of pain (pain area and intensity). This will be evidenced in our

questionnaires (e.g., McGill, PANAS), pain tracking tools, and quantitative sensory tests.

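### For systemic and non-neuropathic pain disorders, a past history bars healthy controls but not migraine patients, so the non-randomised Aim 1 contrast may partly reflect patients' resolved disorders

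*Combined protocol and SAP*

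**What the plan says.** Section 5.1 sets the control criterion: "Without self-reported history of systemic disorders or other pain disorders, including migraine". The migraine criteria in the same section have no corresponding line on past disorders. Patients are covered by the general exclusion in Section 5.2: "Presence of any other systemic or chronic pain disorder".

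Other exclusions in Section 5.2 do look back in time and bind both groups: "History of neurological disorder (e.g. epilepsy, stroke, neuropathy, neuropathic pain" and "History or current evidence of a psychotic disorder (e.g. schizophrenia) or substance abuse".

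The primary outcome (Section 3.3) is that migraine patients have lower thalamic µOR BP_ND at baseline, and that activation "during a sustained thermal pain threshold stress challenge will also be lower than in controls". Controls are matched on age and gender (Section 5.4.1). The Aim 1 model (Section 11.1) adjusts for age and for other nuisance variables, with estradiol and proximity of attacks as examples. Past disorders are not named. Up to 10 of the 30 controls come from an earlier project (Section 4).

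**The concern.** Migraine status is not randomised, so the Aim 1 contrast depends on the two groups being selected alike in everything but migraine. Here they are not. A resolved jaw-pain, back-pain or systemic disorder is compatible with being a migraine patient and incompatible with being a control. Section 5.3 recruits through referral from pain centres and advertising in pain clinics, which makes such histories plausible among patients.

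The protocol also gives a reason to think the imbalance could matter. In Section 11.1 it cites "extensive data from our group showing decreased levels of" µOR BP_ND in chronic pain generally. If any of that deficit persists after the pain resolves, patients would show lower BP_ND for a reason other than migraine. Age and gender matching would not remove the difference. What is at stake is whether a positive primary result can be called specific to migraine.

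**Working it through.** **Step 1: the rules side by side.**

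| Past condition, now resolved | Migraine patient | Healthy control |
|---|---|---|
| Systemic disorder | eligible (5.2 tests presence) | excluded (5.1) |
| Non-neuropathic pain disorder | eligible (5.2 tests presence) | excluded (5.1) |
| Neurological disorder, including neuropathic pain | excluded (5.2) | excluded (5.2) |
| Psychotic disorder or substance abuse | excluded (5.2) | excluded (5.2) |

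Section 5.2 uses history wording where it wants a look-back, so presence most naturally means current. The asymmetry is confined to the first two rows.

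**Step 2: the plan's own figure, for scale.** Section 11.2 states 80% power with 24 per group at an effect size of 1.2, two-sided 0.05. This does not reproduce: a two-sample t-test gives 98.3%, and with 24 per group the effect detectable at 80% power is 0.83 SD. The dropout step does reproduce: 24/(1 − 0.20) = 30. The power mismatch is a separate matter, and nothing below depends on it.

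**Step 3: possible size.** The documents give neither the share p of patients with such a past nor its effect δ on BP_ND in SD units. Both are assumed: p = 20–40%, δ = 0.3–0.8, all in one direction, with no such history in controls.

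- Spurious difference: D = p × δ, from 0.20 × 0.3 = 0.06 to 0.40 × 0.8 = 0.32 SD.
- Chance of a significant result with no migraine effect: power of the two-sided 0.05 t-test at noncentrality D × √(n₁n₂/(n₁+n₂)). The multiplier is √(60×30/90) = 4.47 as enrolled, √(48×24/72) = 4.00 after 20% dropout, and √(24×24/48) = 3.46 for the group sizes in Section 11.2.

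| p | δ | D (SD) | 60 vs 30 | 48 vs 24 | 24 vs 24 |
|---|---|---|---|---|---|
| 20% | 0.3 | 0.06 | 5.8% | 5.6% | 5.5% |
| 20% | 0.5 | 0.10 | 7.3% | 6.8% | 6.3% |
| 30% | 0.5 | 0.15 | 10.2% | 9.1% | 8.0% |
| 30% | 0.8 | 0.24 | 18.6% | 15.7% | 12.9% |
| 40% | 0.8 | 0.32 | 29.3% | 24.3% | 19.2% |

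Mixing two kinds of patient also widens the patient variance by p(1 − p)δ², at most 0.4 × 0.6 × 0.64 = 0.15. That is ignored here.

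**Step 4: direction of the false positives at 60 vs 30.** At 0.06 SD, 4.5% fall in the predicted direction and 1.3% in the other, so 1.3/5.8 = 22% go against the hypothesis. At 0.15 SD about 96% are in the predicted direction, and at 0.32 SD more than 99%.

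**The case against.** The strongest reply is that nothing in the documents shows a bias. The low BP_ND the protocol reports is in chronic pain. Current chronic pain other than migraine already excludes everyone, and no section says that resolved pain leaves a deficit. For past systemic illness the documents give no direction at all. This stands: the bias is possible, not demonstrated.

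A reader might also infer that patients need only be free of other disorders at present, across the board. Section 5.2 contradicts that for neurological disorder (including neuropathic pain), psychotic disorder and substance abuse. Nor do the documents support describing the controls as super-normal, because their criterion rests on self-report.

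Eligibility also differs in another respect. Patients must satisfy "No intake of opiate medication for the past six months", while the only opioid-specific rule for controls is "Current use of opioid pain medications". This shows that the groups differ on more than past disorders, but it does not cancel the point made here.

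Finally, the covariate list in Section 11.1 is open-ended, and Section 11.6 defers the final analysis to a separate Statistical Analysis Plan. Past disorders could still be handled there. That is fair, but the text available does not name them, and an open list does not commit the analysts to including them.

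**Conclusion.** The point holds for systemic disorders and non-neuropathic pain disorders, and only in the non-randomised Aim 1 contrasts. There, the difference between migraine patients and controls may partly reflect patients' resolved disorders, and no matching factor or named covariate guards against it. Active versus sham is unaffected, since both arms are drawn from the same patients under the same rules.

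It is tempting to conclude that the eligibility rules bias the primary outcome towards the hypothesis. The documents support this only conditionally: if resolved pain acts like chronic pain, the bias runs that way. The range of 0.06–0.32 SD rests wholly on assumed inputs. Its upper end needs both upper assumptions at once, and is still about a quarter (0.32/1.2 = 27%) of the planning effect of 1.2 SD. The middle case, 0.15 SD, gives 10% false positives at 60 versus 30 and 8% at 24 versus 24. That is enough to justify an inexpensive check before the result is called specific to migraine. It does not make the comparison invalid.

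**What to change.** 1. Leave the control criterion as it is. Loosening it would not reach controls already scanned. Combined with an analysis that drops only history-positive patients, it would also recreate the imbalance in reverse.
2. From the medical history taken at Screening, code past systemic or other pain disorder (yes/no) in every migraine patient, by the same definition applied to controls and setting aside migraine itself.
3. Prespecify the Aim 1 baseline BP_ND and activation contrasts with history-positive patients removed, reported beside the all-patient contrasts with estimates and confidence intervals. Describe the difference as migraine-specific only if the restricted estimate is similar in size and direction.
4. Confirm whether the up to 10 carried-over controls met the same history rule. Section 14.4 mentions only their demographic and PET/MRI data. If it cannot be confirmed, repeat the restricted contrast without them.

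No new visit or participant is needed. The cost is precision in the restricted analysis. If 30% of patients are removed (0.30 × 60 = 18, leaving 42 versus 30), the difference detectable with 80% power rises from about 0.63 to about 0.68 SD. By the normal approximation this is 2.80 × √(1/60 + 1/30) = 0.63 against 2.80 × √(1/42 + 1/30) = 0.67, and the t-test gives the slightly larger 0.68. If all 10 carried-over controls also had to be dropped, 2.80 × √(1/42 + 1/20) = 0.76, or about 0.77 SD by the t-test.
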